WHO-DD	World Health Organization Drug Dictionary

1 PREFACE

This document describes the planned analyses for the TDE-PH-311 study. This plan is based on the original TDE-PH-311 protocol dated 03 Feb 2012 and subsequent protocol amendments (latest version protocol amendment 6 dated 29 Sep 2016), and provides further details of the analyses presented in the protocol as well as additional planned analyses. Additional post-hoc or unplanned analyses that are not defined in this statistical analysis plan (SAP) may be performed. Such analyses will be documented in the Clinical Study Report (CSR).

2 STUDY OBJECTIVES AND ENDPOINTS

2.1 OBJECTIVES

The objectives of this study are to:

- Provide treprostinil diethanolamine (UT-15C) sustained-release (SR) tablets for eligible subjects who participated in study protocol TDE-PH-310
- Assess the long-term safety of oral UT-15C
- Assess the effect of continued long-term therapy with UT-15C on exercise capacity (6-Minute Walk Distance [6MWD]/Borg dyspnea score), World Health Organization (WHO) Functional Class, and plasma concentrations of N-terminal pro-brain natriuretic peptide (NT-proBNP) (at Week 48 only).

2.2 ENDPOINTS

The safety endpoints are as follows:

- Adverse events (AEs)
- Clinical laboratory parameters
- Vital signs

Concomitant medications, including PAH concomitant medications, also will be documented.

Efficacy will be assessed by:

- 6-Minute Walk Test (6MWT)
- Borg dyspnea score
- WHO Functional Class
- NT-proBNP

3 STUDY DESIGN

This is an open-label study. Subject visits will occur at Baseline, Weeks 6 and 12, and every 12 weeks thereafter. The study will continue until either oral UT-15C becomes available within the respective territories or the study is discontinued by the Sponsor. The Baseline Visit corresponds to the Study Termination Visit from the parent study (TDE-PH-310) and occurs prior to initiation of the open-label study.

4 RANDOMIZATION

This study is not randomized. All subjects will receive UT-15C during the open-label study if the subjects were randomized to UT-15C or placebo in the parent study. However, some analyses are based on the treatment assignment in the parent study.

5 SEQUENCE OF PLANNED ANALYSES

Along with the safety information from the parent study (TDE-PH-310), safety information from the TDE-PH-311 study will be provided to the Data Monitoring Committee (DMC) periodically for safety review.

At the time of study completion and unblinding for the parent study (TDE-PH-310), a data cut for the TDE-PH-311 study will be performed to facilitate the analysis for the TDE-PH-311 study. Analyses based on additional data cuts and the final analyses at the time of study closing will be performed separately.

6 SAMPLE SIZE CONSIDERATIONS

No formal sample size calculation has been conducted. All eligible subjects from the parent study (TDE-PH-310) may be enrolled into this open-label extension study.

7 ANALYSIS POPULATIONS

All available data from all subjects will be used as detailed in this analysis plan.

The safety population will include any subject who received UT-15C at any time during the course of the TDE-PH-311 study. All analyses are based on the safety population.

8 GENERAL CONSIDERATIONS FOR DATA ANALYSES

All data included in each data cut will be listed. In general, listings will be sorted by subject number and scheduled assessment (if applicable) or the visit date. Listings will include assessment date, assessment time (if available), and study day. The study day is calculated as the assessment date minus the date of the first UT-15C dose in the TDE-PH-311 study. For data collected on a fixed schedule, the assessment identifier will also be included on the listing.

In general, the data will be summarized by visit window. The visit window is calculated based on the time from the first dosing date of UT-15C in the TDE-PH-311 study. For all presentations of the summary tables, the data will be presented by subjects in the UT-15C and placebo groups from the parent study (TDE-PH-310) and overall.

For continuous variables, the summary statistics will include the mean, standard deviation, median, minimum, and maximum. Minimums and maximums will be expressed using the level of precision in which the variable was collected. All other statistics will be rounded, using an additional decimal point. For discrete variables, summaries will include the frequency and percent in each category. Percentages will be rounded to 1 decimal point. Whenever practical, categories of discrete variables will be ordered and labeled as they appear in the electronic case report form (eCRF), and all categories represented on the eCRF will be included in summaries, even when they do not apply to any subjects in the study.

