Secondary Objective(s)	
 To assess the long-term safety of oral UT-15C To assess the effect of continued long-term therapy with UT-15C on exercise capacity (6-Minute Walk Distance [6MWD]/Borg dyspnea score), World Health Organization (WHO) Functional Class, and N-terminal pro-brain natriuretic peptide (NT-proBNP) (at Week 48 only)
Exploratory Objective	
 Optional evaluation of pharmacogenomics
Study Design	Multi-center, open-label study for eligible patients who participated in TDE-PH-310
Sample Size	Up to 850 subjects from Protocol TDE-PH-310 will be enrolled.
Summary of Subject Eligibility Criteria	Participation and completion of required visits from TDE-PH-310. Discontinued due to clinical worsening in TDE-PH-310. All ongoing subjects at the time the number of adjudicated clinical worsening (morbidity or mortality) events specified in Protocol TDE-PH-310 has occurred will be eligible to participate in this open-label study.
Drug Dosage and Formulation	
All subjects will receive oral treprostinil diethanolamine (UT-15C) sustained release tablets. Study drug will be provided in 0.125, 0.25, 0.5, 1.0, and 2.5 mg sustained-release (SR) tablets to be administered 3 times daily (TID) immediately after (~10 minutes) consuming food.
 
For subjects who were randomly allocated to UT-15C in TDE-PH-310, the initial dose of UT-15C in the open-label study will be based upon their final dose in TDE-PH-310. Dose escalation of UT-15C may occur in either 0.125 or 0.25 mg increments no more than every 24 hours based on adverse effects and signs and symptoms of PAH.
 
For subjects who were randomly allocated to placebo in Protocol TDE-PH-310, dosing of UT-15C will be initiated at 0.125 mg TID. Dose escalations can occur no more than every 24 hours (3 consecutive doses) in 0.125 mg increments TID during the first 4 weeks of the study. Following 4 weeks

	of treatment, dose escalation may occur no more than every 24 hours in either 0.125 mg or 0.25 mg increments TID every 24 hours. There is no maximum dose specified for this study. Note that sudden dose escalations or reductions may lead to intolerable adverse effects or worsening PAH and gradual dose titrations are recommended to reduce the risk to subjects.
Control Group	None
Route of Administration	Oral

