4 SUBJECT ELIGIBILITY

4.1 INCLUSION CRITERIA

A subject is eligible to participate in this study if all of the following criteria apply:

1. The subject voluntarily provides informed consent to participate in the study.
2. The subject participated in Study TDE-PH-310 and met the definition of clinical worsening (as specified in Protocol TDE-PH-310), remained on study drug, was compliant with study procedures and assessments during the TDE-PH-310 Study or was currently enrolled in that study at the time the study was discontinued by the Sponsor.
3. All WOCBP must practice true abstinence from intercourse when it is in line with their preferred and usual lifestyle, or use 2 different forms of highly effective contraception for the duration of the study, and for at least 30 days after discontinuing study medication. Medically acceptable forms of effective contraception include: (1) approved hormonal contraceptives (such as birth control pills), (2) barrier methods (such as a condom or diaphragm) used with a spermicide, (3) an intrauterine device, or (4) partner vasectomy. For women of childbearing potential, a negative urine pregnancy test is required at Baseline (study entry) prior to initiating study medication. WOCBP includes any female who has experienced menarche and who has not undergone successful surgical sterilization (hysterectomy, bilateral tubal ligation, or bilateral oophorectomy) or is not postmenopausal (defined as amenorrhea for at least 12 consecutive months).
4. Males participating in the study must use a condom during the length of the study, and for at least 48 hours after their last dose of study medication.

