4.2 EXCLUSION CRITERIA

A subject is not eligible to participate in this study if any of the following criteria apply:

1. The subject is pregnant or lactating.
2. The subject has received infused or inhaled prostacyclin therapy for 29 days or more.
3. The subject was prematurely discontinued from Study TDE-PH-310 for reasons other than a clinical worsening event.
4. The subject developed a concurrent illness or condition during the conduct of TDE-PH-310 which, in the opinion of the Investigator, would represent a risk to overall health if they enrolled in this study.

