11.3 DEATHS

All deaths will be listed (including those occurring within 30 days of the last UT-15C dose) by subject, and will include the subject number, treatment group in the parent study, date of assessment (day), whether subject died, date of death (day), and cause of death (including other, specify text [if applicable]). An additional listing of deaths will include the subject number, first UT-15C dose in TDE-PH-311 study, last UT-15C dose (day) in TDE-PH-311 study, date of death (day), and cause of death. The summary of deaths will be presented by the parent study and overall and will include the number (percent) of subjects who died (including those within 30 days of study participation) and their causes of death.

Time to death will be calculated as:

(the death date – the date of the first UT-15C dosing in TDE-PH-311 study)

The Kaplan-Meier (K-M) estimator will be provided for the time to death, and K-M plots will be provided by treatment group in the parent study.

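### Visit summaries and the time-to-death curve are not split by entry route, so at data cuts soon after parent closure the later rows and curve segments may describe clinical-worsening entrants alone

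*SAP*

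**What the plan says.** **Who enters.** The Protocol Synopsis admits subjects who "Discontinued due to clinical worsening in TDE-PH-310" and "All ongoing subjects at the time the number of adjudicated clinical worsening (morbidity or mortality) events specified in Protocol TDE-PH-310 has occurred". Inclusion criterion 2 (Protocol 4.1) covers a subject who met the parent's definition of clinical worsening "or was currently enrolled in that study at the time the study was discontinued by the Sponsor". Protocol 4.2 bars anyone of whom this is true: "The subject was prematurely discontinued from Study TDE-PH-310 for reasons other than a clinical worsening event".

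**When data are cut.** SAP 5: "At the time of study completion and unblinding for the parent study (TDE-PH-310), a data cut for the TDE-PH-311 study will be performed". It adds: "Analyses based on additional data cuts and the final analyses at the time of study closing will be performed separately". No dates are given for the later cuts.

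**How results are grouped.** SAP 8 sets the general rule: "the data will be presented by subjects in the UT-15C and placebo groups from the parent study (TDE-PH-310) and overall". SAP 10.1 adds etiology, Baseline WHO class and last-dose quartile for 6MWD. SAP 10.2 and 10.3 present Borg score and WHO class by parent arm. For time to death, counted from the first UT-15C dose in TDE-PH-311, SAP 11.3 says "K-M plots will be provided by treatment group in the parent study". No title in SAP 12.1 to 12.3 mentions entry route, and SAP 8.1 allows exploratory subgroups without naming a factor.

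**The concern.** The two routes run on different calendars. A worsening entrant can start TDE-PH-311 well before the parent closes; a closure entrant cannot. At any cut, the longest follow-up of a closure entrant is the time since closure, so administrative censoring depends on route. K-M estimation pooled across routes needs censoring to be unrelated to the risk of death, and that fails if the routes differ in mortality. A visit table has the same weakness without the formal assumption: the subjects in a late row need not resemble those in an early row.

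Protocol 10.3 promises an examination of how safety and efficacy data move over time, and Protocol 2.2 has a secondary objective on the effect of continued long-term treatment. A reader following an arm down the visit rows, or along its survival curve, could mistake a change in membership for a change in patients' condition.

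**Working it through.** The plan states no figure to reproduce. The check has two parts: bookkeeping that needs no assumed rates, and an illustration that does.

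**1. Composition of rows and risk sets.** Let T be the time from parent closure to the cut.

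- Closure entrant: maximum follow-up = T.
- Worsening entrant who started a time e before closure: maximum follow-up = T + e.
- On the two-route reading, therefore, any row or risk set beyond about T holds worsening entrants only.

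SAP 8.4 uses nominal visits, and Protocol 3.2 (footnote c) allows ±14 days. Closure entrants can then first appear:

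- in the Week 24 row at 24 − 2 = 22 weeks after closure;
- in the Week 48 row at 48 − 2 = 46 weeks after closure.

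SAP 8 says instead that data are summarized by visit window, of unstated width. Under that rule these two times are unknown.

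Example of the step, ignoring the ±14 days. The 850 is the protocol's maximum. The 25% worsening share, uniform entry over the 2 years (104 weeks) before closure, a 12-week T and no dropout are assumed.

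- Week 12 row: 0.25 × 850 ≈ 212 worsening and 638 closure entrants (25% worsening).
- Week 24 row: 212.5 × (1 − 12/104) ≈ 188 worsening and 0 closure entrants (100% worsening).

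**2. Illustrative effect on the K-M curve within one arm.** Assumed: worsening share w; 1-year mortality m_W (worsening) and m_C (closure), constant hazards; all closure entrants dosed at closure; some worsening entrants followed past t. Up to T both routes are at risk in full; after T only the worsening hazard acts. For t > T:

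- K-M(t) = [w(1 − m_W)^T + (1 − w)(1 − m_C)^T] × (1 − m_W)^(t − T)
- Comparator: survival of the dosed mix, w(1 − m_W)^t + (1 − w)(1 − m_C)^t

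Set A: w 0.25–0.45, m_W 0.15–0.20, m_C 0.04–0.05. For T = 0.25 and t = 1 year:

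- Largest gap (w 0.25, m_W 0.20, m_C 0.04): (0.25 × 0.9457 + 0.75 × 0.9898) × 0.8459 = 0.828, against 0.25 × 0.80 + 0.75 × 0.96 = 0.920. Gap 9.2 points.
- Smallest gap (w 0.45, m_W 0.15, m_C 0.05): (0.45 × 0.9602 + 0.55 × 0.9873) × 0.8853 = 0.863, against 0.905. Gap 4.2 points.

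Set A implies whole-arm 1-year mortality of 6.8–11.8%. The only survival figure in the documents is 93.6% at 1 year in TDE-PH-304, a different extension population (Protocol 1.2.4), which is 6.4% mortality. Set B therefore fixes the whole arm at 6.4% and lets worsening mortality be r = 2 to 4 times closure mortality: m_C = 0.064/(wr + 1 − w), m_W = r × m_C.

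| Cut after closure | Estimate | A: points low | B: points low |
|---|---|---|---|
| 3 months | 1-year | 4.2–9.2 | 1.8–6.3 |
| 6 months | 1-year | 2.8–6.3 | 1.2–4.2 |
| 1 year | 1-year | 0 | 0 |
| 1 year | 2-year | 5.2–11.5 | 2.3–7.9 |
| 2 years | 2-year | 0 | 0 |

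At the 3-month cut under A, worsening entrants are 24–44% of those at risk just before 3 months and 100% just after. With r = 1 every gap is 0; if worsening entrants die less often, the sign reverses.

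For scale, the 95% half-width of the pooled 1-year K-M at the 3-month cut is 4.9–7.6 points (A) or 3.9–6.7 (B). This is 1.96 × Greenwood standard error, with 425 per arm and worsening entry assumed uniform over 2.5–4 years before closure. The shift is comparable with sampling error, but more subjects would not shrink it.

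**The case against.** **The word only.** It depends on a parent protocol that is not supplied. The Synopsis also lists completion of the parent's required visits, and Protocol 1.4 speaks of subjects who have completed TDE-PH-310. If the parent let subjects finish before closure without worsening, they too could fill late rows. The Synopsis ties ongoing subjects' entry to the event count, so the two-route reading is the more natural one, but it remains a condition.

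**Route is not hidden.** The disposition listing in SAP 9.1 gives first-dose and cut-off dates, which set against the parent's closure date largely identify route. That stands. What is missing is a summary or figure that shows it.

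**Nothing is tested.** Access to drug is the primary objective (Protocol 2.1) and no hypothesis test is planned (Protocol 10.3). SAP 8.1 leaves room for subgroups, and the 6MWD split by Baseline WHO class is a partial severity split. All true. These points limit the harm to description, but none commits the plan to showing route.

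**Size is assumed.** Route shares, mortality by route and cut dates after parent completion are all absent from the documents. The effect at a given time disappears once closure entrants have been followed that far, in a study expected to run about 6 years (Protocol 3.6). This also stands.

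**Deaths table.** Table 14.3.2.2 counts deaths and causes without visit rows or a time axis, so the late-row argument does not reach it.

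**Conclusion.** The plan groups by parent arm and has no display by entry route, although its entry rules and its first cut make follow-up depend on route. On the two-route reading, rows and risk sets beyond the time since closure hold worsening entrants only. Plotted survival past that point still carries the earlier mixed segment.

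Whether this misleads depends on the routes differing in mortality or in change from Baseline. If they do not, there is no effect. Under the assumed inputs the 1-year K-M is about 2 to 9 points low at a 3-month cut and unaffected at a 1-year cut. No figure can be given for 6MWD, Borg score or WHO class.

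A reader might infer that the survival curve is known to be biased downward, or that the long-term results as a whole are unreliable. The documents support neither: they give no outcome by route, and the problem is confined mainly to early cuts and late tails. The change is worth making because it is cheap; confidence is medium.

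**What to change.** In SAP 8, 10.1 to 10.3 and 11.3:

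- Derive entry route (clinical worsening, or ongoing at parent closure) from parent disposition data. The SAP 9.2 listing records rollover, not route. State how any subject who fits neither category is classified.
- At each cut, report counts by route, parent arm and visit.
- Present Tables 14.2.1.1 (6MWD), 14.2.1.2 (Borg) and 14.2.1.8 (WHO class) and Figure 14.2.1 by route within parent arm, at least at cuts where closure entrants have not reached the displayed visits or times.
- Under any K-M curve pooled across routes, print numbers at risk by route, and do not interpret the curve beyond the follow-up closure entrants have reached.
- Splitting Table 14.3.2.2 is optional.

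The cost is SAP wording, one derived variable, a few repeated displays and smaller strata. If all 850 enter in equal arms of 425 with 25–45% worsening, each arm has about 106–191 worsening and 234–319 closure entrants. Under Set A the 95% half-width for 1-year survival of worsening entrants is 5.3–8.2 points at a 3-month cut (5.1–7.6 if fully observed). For fully observed closure entrants it is 2.2–2.8 points. No new data collection or change in conduct is needed.

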8.1 EXAMINATION OF SUBGROUPS

Exploratory subgroup analyses will be performed as data permit.

8.2 PREMATURE DISCONTINUATION AND MISSING DATA

A subject may voluntarily withdraw or be withdrawn from the study by the Investigator at any time for reasons including, but not limited to, the following:

- The subject wishes to withdraw from further participation.
- A serious or life-threatening AE occurs or the Investigator considers that it is necessary to discontinue study drug to protect the safety of the subject.
- The subject deviated from the protocol.
- The subject's behavior is likely to undermine the validity of his/her results.

- The subject becomes pregnant

All available data from all subjects in the safety population, as defined in Section 7, will be used as detailed in this analysis plan.

Missing data will not be imputed.

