TDE-PH-304 is a long-term, open-label, international, Phase 3 studies designed to provide access to UT-15C for subjects previously enrolled in studies TDE-PH-301, TDE-PH-302, TDE-PH-308, or other specified studies conducted during the UT-15C development program. Secondary objectives of the study are to assess the long-term safety of UT-15C in PAH patients and to assess the effect of continued therapy on exercise capacity via 6MWD following one year of treatment with UT-15C. As of 01 September 2015, over 896 subjects were enrolled, representing 2377.7 patient-years of exposure. The mean and maximum duration of exposure was 138.8 and 444.9 weeks (2.66 and 8.53 years), respectively. The mean dose of oral treprostinil achieved was 3.9, 4.5, 4.8, 5.0, 5.5, 5.9, and 5.9 mg BID at 1 year (N=605), 2 years (N=472), 3 years (N=337), 4 years (N=230), 5 years (N=119), 6 years (N=77), and 7 years (N=37), respectively. Adverse Events were typical of prostacyclin

therapy; laboratory findings were unremarkable and did not suggest any specific safety concerns related to long-term treatment with UT-15C. Following 12 months of oral treprostinil treatment, the mean 6MWD increased by +25 meters as compared with Baseline. Kaplan-Meier analysis of subject survival demonstrated 1-, 2-, and 3-year survival estimates of approximately 93.6%, 87.9%, and 82.2%, respectively.

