8.4 ASSESSMENT WINDOWS

For efficacy and safety assessments, Baseline is defined as the measurements prior to the first dose of UT-15C in the TDE-PH-311 study.

Summary analyses will be based on the scheduled (nominal) visits with no visit windows applied.

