10 EFFICACY ANALYSES

10.1 6-MINUTE WALK TEST

The listing of the 6MWT will be organized by treatment group in the parent study, and will include subject number, analysis visit, assessment date/time (day), last UT-15C dose date/time (day), the last UT-15C dose (in milligrams), hours from last UT-15C dose to 6MWT, 6MWD results, Borg dyspnea scores, use of supplemental oxygen, and any circumstances affecting the 6MWT. The summaries of 6MWD will be provided by treatment assignment in the parent study (UT-15C or placebo) by visit, PAH etiology (idiopathic, heritable, associated with connective tissue disease, and other), Baseline WHO Functional Class, and quartiles of the last UT-15C dose. The summaries will include descriptive statistics for 6MWD measure at each analysis visit and the change from Baseline. Baseline is defined as the last 6MWD measured prior to the first dose of UT-15C in the TDE-PH-311 study.

Achievement of a walk distance of at least 440 m by each analysis visit will be summarized by treatment group in the parent study and overall. Achievers and non-achievers will then be summarized based on their Baseline walk (≤ 440 m vs >440 m) by treatment group in the parent study and overall.

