10.2 BORG DYSPNEA SCORE

Borg dyspnea score information will be listed as part of the 6MWD. The summary of the Borg dyspnea score will be provided by treatment group in the parent study. The summaries will include descriptive statistics for measurements at each analysis visit and the change from Baseline values. Baseline is defined as the last Borg dyspnea score measured prior to the first dose of UT-15C in the TDE-PH-311 study.

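### By-visit 6MWD and Borg summaries rest only on subjects who walked at that visit, with no supportive analysis for death or withdrawal, so the long-term trend may be biased upward; the 440 m denominator is not stated.

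*SAP*

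**What the plan says.** SAP 8.2 gives the whole missing-data rule in two sentences: "All available data from all subjects in the safety population, as defined in Section 7, will be used as detailed in this analysis plan", and "Missing data will not be imputed".

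For the walk, SAP 10.1 says "The summaries will include descriptive statistics for 6MWD measure at each analysis visit and the change from Baseline". For Borg, SAP 10.2 says "The summaries will include descriptive statistics for measurements at each analysis visit and the change from Baseline values". WHO Functional Class (SAP 10.3) has the same form. SAP 8.4 adds "Summary analyses will be based on the scheduled (nominal) visits with no visit windows applied". A subject without a walk at a visit therefore contributes nothing to that visit.

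On the 440 m threshold, SAP 10.1 says "Achievement of a walk distance of at least 440 m by each analysis visit will be summarized by treatment group in the parent study and" for the groups pooled. It names no denominator and does not say how a subject without a walk is classed. SAP 7 says "All analyses are based on the safety population".

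The output list in SAP 12.1 (Tables 14.2.1.1 to 14.2.1.8) has no efficacy table that takes death or discontinuation into account. Those are reported apart from the walk data: disposition in SAP 9.1, and deaths with Kaplan-Meier time to death in SAP 11.3.

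The protocol makes the effect of long-term therapy on exercise capacity a secondary objective (2.2) and has the data examined for trends over time, without hypothesis tests (10.3). Subjects who go on to permanent prostacyclin therapy must leave (4.3.1). A walk is planned at the Study Termination Visit (3.3.1.1, 7.1.5), but the SAP does not say how it enters the by-visit tables.

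**The concern.** With one open-label arm, the course of 6MWD over time is itself the efficacy result, and it is computed on a set of subjects that shrinks and changes over about six years. Some exits are plausibly linked to decline: death, a serious adverse event, and the mandatory exit on permanent prostacyclin therapy. If those subjects had been losing distance, removing them raises the mean change among the rest, and the rise grows as losses accumulate. A reader of the by-visit table could not tell a sustained benefit from a change in who is being measured. The earlier extension's headline of +25 m at 12 months (Protocol 1.2.4) is the kind of figure this plan would produce.

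The 440 m percentage has a further problem. Its meaning depends on a denominator that is left open, and so does the direction in which attrition moves it.

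**Working it through.** The plan has no sample size, power or target effect to reproduce. The check asks how far an observed-case mean can move.

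**Inputs from Protocol 1.2.4 (earlier extension, TDE-PH-304, used as a proxy).** Survival was 93.6%, 87.9% and 82.2% at years 1, 2 and 3. Over 896 subjects were enrolled, with 2377.7 patient-years. Dose data were available on 605 subjects at year 1 and 337 at year 3. Mean 6MWD change at 12 months was +25 m. Coherence check: 2377.7/896 = 2.65 years, against a stated mean of 2.66.

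**Formula.** Let p be the share observed and D the mean change of those observed minus that of those missing. Then observed mean minus all-subject mean = (1 − p) × D. D is not in the documents; I take 20, 40 and 80 m. For subjects who died, D is a notional deficit, since they have no walk to measure.

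**Deaths only**

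| Year | 1 − p | D = 20 | D = 40 | D = 80 |
|---|---|---|---|---|
| 1 | 0.064 | 1.3 m | 2.6 m | 5.1 m |
| 2 | 0.121 | 2.4 m | 4.8 m | 9.7 m |
| 3 | 0.178 | 3.6 m | 7.1 m | 14.2 m |

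**All subjects without dose data treated as informative (an upper case)**

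| Year | p | 1 − p | D = 20 | D = 40 | D = 80 |
|---|---|---|---|---|---|
| 1 | 605/896 = 0.675 | 0.325 | 6.5 m | 13.0 m | 26.0 m |
| 3 | 337/896 = 0.376 | 0.624 | 12.5 m | 25.0 m | 49.9 m |

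This case overstates the loss, because it includes subjects who had not yet reached that time. If D = 0 the shift is zero. If leavers did better by 20 m, the shift runs from −1.3 m (deaths only, year 1) to −12.5 m (upper case, year 3).

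**A second model.** Assume SD of change 75 m, no true change, and log-odds of dropout rising by 0.3 to 0.8 per SD of decline. The observed mean change is then about +4 to +11 m at 20% loss and +9 to +21 m at 40% loss. All of these inputs are assumed, all loss is taken as informative, and the result scales with the SD.

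**What drives the loss matters.** Simulation with 400,000 subjects, no true change and 67.5% observed. Baseline mean is 346 m (the TDE-PH-301 figure in Protocol 1.2.4). Assumed: baseline SD 90 m, SD of change 60 m, log-odds of dropout 1 per SD. The true share at or above 440 m is 19.1%. In the last column a subject without a walk counts as a non-achiever.

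| Loss depends on | Raw mean minus truth | Mean change | 440 m, attendees | 440 m, safety population |
|---|---|---|---|---|
| Nothing | +0.1 m | +0.1 m | 19.2% | 13.0% |
| Baseline walk only | +24.5 m | 0.0 m | 24.6% | 16.6% |
| Change only | +16.4 m | +16.4 m | 23.0% | 15.5% |
| Current walk | +29.4 m | +9.1 m | 25.6% | 17.3% |

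Two things follow. Mean change is paired within subject, so loss that depends only on baseline inflates the visit mean and leaves the mean change alone; the SAP reports both. And when poorer walkers leave, the 440 m percentage goes above the truth on the attendee denominator and below it on the safety-population denominator.

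**The case against.** The strongest reply is that the direction is not established. Change from Baseline is paired, a walk is planned at exit for leavers other than deaths, and much of the missingness will be administrative: data cuts (SAP 5), drug becoming available in a territory, or closure by the sponsor (SAP 3). The proxy is another study, dosed twice daily, whose yearly counts mix deaths, withdrawals and subjects not yet due. Attrition is also visible in SAP 9.1 and 11.3, and the analysis is descriptive with drug supply as its primary objective, so no error rate is at risk.

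Most of this stands, and it limits the point. It does not remove it: disposition and survival are never linked to the walk results, and the SAP leaves the exit walk without a role.

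Three stronger readings are tempting, and the documents do not support them:
- A reader might infer that the long-term results must improve as subjects leave. The table above shows zero bias in mean change under two of the four mechanisms.
- A reader might infer that the 440 m percentage is computed on attendees. SAP 10.1 gives no denominator, and SAP 7 points towards the safety population. The wording can also be read as cumulative achievement.
- A reader might infer that the bias is worse because subjects can enter after clinical worsening. Their Baseline is taken at the parent study's termination visit, so poor status at entry is already in it. At the first data cut, late visits may come mainly from such early entrants, which could pull results down.

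**Conclusion.** The point holds in conditional form. The by-visit 6MWD and Borg results are observed-case, and no planned output shows how far death, withdrawal or mandatory exit contributes to the trend. If leavers are declining, the mean 6MWD change is biased upward by about 1 to 5 m at year 1 and 4 to 14 m at year 3 from deaths alone. This rests on the earlier extension's survival applying here and on leavers doing 20 to 80 m worse. The bias is larger if other exits are informative; in the upper case at year 1 with D = 80 m it reaches 26 m, about the whole +25 m reported in that extension. It is nil if loss is unrelated to change. Separately, the 440 m result cannot be interpreted until its denominator is stated. What is at stake is the reading of a secondary descriptive objective, not a test.

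**What to change.** Keep the observed-case tables and add three things to the SAP.

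1. **One supportive Week 48 summary.** Report the median 6MWD change in subjects dosed early enough to reach Week 48 by the cut-off. Rank lowest the deaths and the exits for a pre-listed set of disease-related reasons, including permanent prostacyclin therapy. For other leavers use the termination-visit walk where there is one, and report how many have neither. The set must be written down, because the withdrawal reasons in Protocol 8.1 and SAP 8.2 are not exhaustive and include no category for worsening.
2. **A defined 440 m analysis.** The denominator is safety-population subjects due at the visit. Count death and non-administrative discontinuation as non-achievement. Exclude exits for commercial availability or sponsor closure from visits after the exit, so that a stable walker who moves to commercial drug is not scored as a failure. State whether achievement is at the visit or cumulative.
3. **A per-visit account.** Give the number observed, dead, withdrawn, administratively exited and not yet due, with the baseline of the subjects observed.

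Deciding who is due also needs SAP 8 (visit windows) reconciled with SAP 8.4 (nominal visits, no windows).

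The cost is SAP wording and two small tables, using assessments and exit reasons already planned for collection. The supportive figures are likely to be less favourable than the observed-case ones.
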